The goal of this proposal study is to develop and test a model of CHW health coaching, designed to prevent the onset of Type 2 DM in a large population of underserved patients at risk. CHWs will be recruited from the target populations and trained in core competencies to serve as peer health coaches. Our central premise is that CHWs are uniquely suited to engage fellow patients by encouraging lifestyle change through shared experiences and social support to extend the reach of primary care (PC) beyond the clinic visit. This study will test a scalable model of peer health coaching to address the millions of patients at risk for DM, using low cost, culturally congruent personnel to promote prevention of DM in PCMH practice.

Background

Type 2 DM is a preventable chronic disease that affects 11% of US adults. An additional 35% (79 million) have pre-DM and thus at risk of developing DM and cardiovascular disease. DM is a leading cause of death in the US and a major cause of heart disease and stroke. It is essential that the US leverage prevention strategies to mitigate the health and economic impact of DM in the population. Up to 20% of adult PC patients at BH and 25% of veterans at NY Harbor have DM, 2x and 3x the rate in the general population, respectively, and this rate has been steadily increasing. There is also a substantial population with undiagnosed pre-DM, half of who are expected to develop DM in the next decade. Our preliminary analysis of VA NY Harbor data from 2010-2012 showed that 9,610 (62%) of 15,500 veterans <75 years old, without DM, had a glycosylated hemoglobin (HbA1c) test, and 1,730 (18%) of them had pre-DM.

Study Design

We will conduct a cluster-randomized trial to test the impact of peer health coaches on prediabetic patients cared for by PCMH teams at BHC and VA to:

1. Reduce the incidence of type 2 DM in pre-diabetic, PCMH patients;
2. Promote weight loss among pre-diabetic patients;
3. Increase patient activation levels, a measureable construct of engagement, efficacy, skills, and confidence in managing one's health, among pre-DM patients, resulting in:
 - a. Improved secondary clinical outcomes: better glycemic and blood pressure control, and lower Framingham risk scores;

- b. Increased utilization of preventive services (e.g. MOVE!, TeleMOVE!, Healthy Lifestyles, etc.);
- c. Improved health behaviors (e.g. making dietary and exercise changes); and

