- 4. Develop, implement and assess strategies to recruit, train, and integrate peer CHW health coaches within the PCMH model.

The 36-month intervention will be conducted using a staggered entry design across four, overlapping, 12-month waves to account for CHW caseload limits. This study will test a scalable model of peer health coaching to address the millions of patients at risk for DM, using low cost, culturally congruent personnel to promote prevention of DM in PCMH practice. If successful, our study team will work with VA's Central Office and NY City's Health and Hospital Corporation to translate the model for larger scale implementation.

Characteristics of the Research Population

Number of Subjects

All 12 PC teams at VA NY Harbor and all 4 PCMH teams at BH will be eligible to participate. In our VA PROVE study, 51/52 PCPs participated in the intervention, and we expect similar rates in this project. Eligible patients will be identified through the study's pre-DM registry, which will be based on the EMR and Corporate Data Warehouse (CDW) at each site. This methodology builds on our ongoing national, retrospective cohort study of predictors of DM among veterans with pre-DM back to 2008. Based on preliminary analysis of VA NYHHS data from 2010-2012, 62% of veterans enrolled in PC without DM, have had an HbA1c test in the previous two years.

In the intervention group, we anticipate contacting 2,100 randomly selected patients (1,050 at the VA* and 1,050 at BH) to ultimately enroll about 1,100 patients (550 at the VA and 550 at BH). This outreach sample reflects our assumption that 20% of patients will be unreachable and that 60% of those reached will enroll in the study. Another 1,100 patients attributed to control group providers will be randomly selected as the control group, in accordance with the waiver of HIPAA authorization. As detailed below, the control group will not participate in the CHW intervention. The total sample, including the intervention and control groups, will be about 2,200 patients. This amounts to approximately 265 patients (across intervention and control groups) per wave and per clinical site.

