Influence of neighborhood factors: To examine the influence of contextual factors on implementation and intervention effectiveness, we will conduct population-level analysis of variation in implementation and health outcomes across NYC neighborhoods. We will conduct this analysis with patient data available at the start of the study and data on enrolled patients post-intervention. To obtain information on neighborhood-level factors, we will use publically available data on social and environmental aspects of NYC neighborhoods in the FACETS database (data accessible at <https://github.com/mcantor2/FACETS>). We will map patient addresses to census tracts, aggregate census tracts to neighborhoods, and statistically examine the association of neighborhood-level contextual factors on prediabetes prevalence across NYC. Patients' location information will be used at an aggregate neighborhood level, and it will not be possible to identify their precise location in the city. Individual patients and their PHI will not be identifiable.

Data Analysis and Data Monitoring

The analytic methods described below are designed to test the primary hypotheses that prediabetic patients cared for by PCMH teams randomly allocated to the CHW Coaching group, will have lower annual hazard rate of incident cases of DM overtime more weight loss, and higher PAM scores by the end of the intervention

period than similar patients cared for by PCMH teams allocated to the Control group, adjusting for baseline rates. The unit of analysis is patients, aggregated to the provider level.

Analysis: Patient Clinical Outcomes and Health Behaviors

Descriptive analysis techniques (measures of central tendency and variability, frequencies and proportions) will be used to present baseline characteristics of participants (patients and their PC staff) in the control and intervention arms. Chi-square tests and t-tests will be used to check if these baseline characteristics are balanced between the two study groups. For continuous outcomes, normal assumptions will be checked, and non-parametric alternatives and transformations will be considered as needed.

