To assess the overall effectiveness of the CHW intervention we will compare cumulative DM incidence rates and time to DM incidence (in addition to other outcomes: weight loss, obesity rate, and health care utilization) between the two study groups, using intention-to-treat and per protocol analyses. Time to DM incidence at 12-month follow-up of the intervention and control arms, aggregated across the 4 study waves, will be compared using Cox proportional hazard regression models. Chi-square analyses will be conducted to compare outcomes between the two groups for categorical variables (e.g. obesity rate, PAM stage) and t-tests will be conducted for continuous outcomes (e.g. weight change, PAM score). We will then conduct (generalized) linear mixed-effects modeling, which will (1) take into account the intra-cluster correlation coefficient (ICC) of patients within providers and teams, (2) analyze repeated measures at several time-points (baseline, midpoint, and post-intervention) simultaneously, (3) include team or patient level baseline covariates easily, if they are found to be unbalanced between two arms, and (4) deal with attrition problems and other missing data automatically. For categorical outcomes, such analyses will be implemented using SAS Proc GLIMMIX, while using SAS Proc MIXED for continuous outcomes.

We will use multilevel survival analysis to determine the effect of the intervention on time to DM, as patients are enrolled in waves and the time to DM incidence may be censored by the end of study. Specifically, we will fit Cox proportional hazard regression models with mixed effects to examine the hazard ratio between two groups, adjusting for important covariates and taking into account the correlation among patients within teams.

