Data from the FACETS neighborhood database of social determinants will be conjoined with study data to describe whether contextual factors pertaining to NYC neighborhoods are associated with prediabetes prevalence across neighborhoods. We will use a multilevel statistical model, with patients nested within neighborhoods, to conduct this analysis.

Process Evaluation: To ensure that the intervention was delivered completely and standardized across the sites, CHWs and clinical teams, there will be continuous monitoring of process outcomes and fidelity to the protocol during the CHW intervention. We will maintain standardized protocols for each toolkit strategy and documentation of peer coaching. The CHW Coordinator will conduct quarterly assessments of the interventions, proportion of patients reached and engaged by site and CHW, fidelity to counseling protocols, and the preferred toolkit and contact strategies.

Statistical Power and Sample Size

The primary study outcome for power calculations is the annual hazard rate of incident DM.

To determine sample size, we begin with the total accessible population of about 46,000 primary care patients served at the two sites (BH and VA). Of these we exclude patients with diagnosed DM (25% at VA and 15% at BH) and those over 75 years of age (who are ineligible for this intervention). Of these eligible subjects, we estimated that about 70% will have had the HbA1c test in the last 2 years and that about 40% of these will have had a test result in the prediabetes range.

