While the above inclusion and exclusion criteria return about 9,300 eligible patients, 8,200 at BH and 1,100 at the VA, CHW caseload limitations preclude us from reaching all these eligible patients during the 3-year intervention. Assuming a caseload of 72 patients per fulltime CHW per wave (with 3.5 fulltime equivalent CHWs across both sites and 4 waves), the intervention is projected to enroll a minimum of 1,008 subjects into the intervention group. An equivalent number of subjects will be randomly selected from the Control teams for a total of at least 2,016 study subjects overall. The intervention and control subjects will be split across the two study sites. After assuming that we will not be able to reach about 20% (due to missing or incorrect contact information) unreachable rate, and that about 60% will consent to enroll in the intervention, we will randomly select about double the 1,008 subjects (about 2,100) for potential enrollment into the intervention in order to enroll the minimum of 1,008 intervention subjects needed to have adequate statistical power.

Power: In the pre-DM population we estimate the 3-year DM incidence to be 15% (based on preliminary analysis of a similar VA cohort from 2010-2012). Based on our analyses, with 1,008 patients allocated to each of the intervention and control groups, we anticipate having 80% power ($\alpha = 0.05$) to detect a difference in time-to-event (DM incidence) between the intervention and control group.

To assess measures of implementation fidelity, specifically coverage, duration, and frequency of CHW-patient contact, we will base calculations on all patients enrolled. Since we will use all available study data from the electronic medical records, power and sample size considerations do not apply. We will assess content of CHW-patient contact using qualitative methods, hence power and sample size considerations do not apply.

To examine the variation in prediabetes prevalence across NYC neighborhoods, we will use available data from BH at the start of the study, in approximately 19,000 patients. These patients meet the study's previously stated eligibility criteria, with two modifications: patients must have (1) any HbA1c result in the past 5 years and (2) an address available in the EHR. Data on all enrolled BH patients at the end of the study, an estimated 1,000 patients, will also be used. Since we will use all available study data, power and sample size considerations do not apply.

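### The enrolment figures in Number of Subjects do not follow from their own inputs, the VA targets conflict with the VA eligible count, and the 80% power is stated without an effect, horizon, design effect or attrition

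*Combined protocol and SAP*

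**What the plan says.** **Design.** Study Design: "We will conduct a cluster-randomized trial to test the impact of peer health coaches on prediabetic patients". Number of Subjects: "All 12 PC teams at VA NY Harbor and all 4 PCMH teams at BH will be eligible to participate", so at most 16 randomised units.

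**Power.** Statistical Power and Sample Size names the outcome: "The primary study outcome for power calculations is the annual hazard rate of incident DM". The event rate is "In the pre-DM population we estimate the 3-year DM incidence to be 15" (per cent), and the claim is that "with 1,008 patients allocated to each of the intervention and control groups, we anticipate having 80% power". The effect is described only as a difference. The section derives 1,008 from community health worker (CHW) caseload and also calls it the minimum needed for adequate power.

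**Follow-up.** Data Analysis and Data Monitoring states the hypothesis that intervention patients "will have lower annual hazard rate of incident cases of DM overtime". Analysis: Patient Clinical Outcomes and Health Behaviors compares "Time to DM incidence at 12-month follow-up of the intervention and control arms, aggregated across the 4 study waves", and in its next paragraph says "the time to DM incidence may be censored by the end of study".

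**Sample.** Number of Subjects gives 2,100 contacts (1,050 per site), 20% unreachable, 60% consent among those reached, about 1,100 enrolled (550 per site), 1,100 controls, 2,200 in total, and about 265 per wave per site over both arms. Statistical Power and Sample Size applies the same contacts and rates to 1,008 enrolled and at least 2,016 in total. It counts 8,200 eligible at Bellevue (BH) and 1,100 at the VA, and names caseload as the limit. CHW Intervention plans outreach to about 250 patients per site per wave.

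**The concern.** Diabetes incidence is the outcome on which the trial is sized. If the result is null, a reader will ask what effect the trial could have detected, and the plan does not say. The answer depends heavily on the follow-up used. At a constant hazard, 12 months yields about a third of the events of 3 years. Team randomisation and loss to follow-up both reduce the information further, and neither appears in the power text.

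The sample figures matter for a different reason. Two sections give different enrolment from identical inputs, so there is no single target to report against. If the VA cannot supply its half, the site mix changes, and with it the average team size and the design effect.

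**Working it through.** **1. Figures that reproduce**
- Caseload: 72 × 3.5 full-time equivalents × 4 waves = 1,008. Doubled: 2,016.
- Contacts: 1,008 / (0.8 × 0.6) = 2,100.

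**2. Figures that do not**
- 2,100 × 0.8 × 0.6 = 1,008, not 1,100. Enrolling 1,100 needs 1,100 / 0.48 ≈ 2,292 contacts. Per site, 1,050 × 0.48 = 504, not 550.
- 265 × 2 sites × 4 waves = 2,120. A total of 2,200 would be 275 per wave per site; 2,016 would be 252.
- 250 contacts × 2 × 4 = 2,000, not 2,100.

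**3. VA feasibility**
- Planned: 1,050 contacts + 550 controls = 1,600, against 1,100 eligible. The 550 is inferred from the even site split; with 504 controls the sum is 1,554.
- Arms draw on different teams, so patients cannot be moved between them. If half of the 1,100 sit in intervention teams (assumed), 550 × 0.48 = 264 would enrol, against 504 to 550 planned.
- The count is itself doubtful. Background reports 1,730 VA patients under 75 with pre-diabetes. Half of those gives 865 × 0.48 ≈ 415, still below 504.
- Applying the sizing percentages (70% tested, 40% of those in range) to the 30,000 BH patients in Purpose of the Study: 30,000 × 0.85 × 0.70 × 0.40 = 7,140 at most, before the age exclusion, against 8,200 stated. For the VA: (46,000 − 30,000) × 0.75 × 0.28 = 3,360 before the age exclusion, against 1,100. The share over 75 is not given, so this does not rule out 1,100.

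**4. Power**

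The plan's 80% cannot be reproduced, because no hazard ratio (HR) is given. Assumptions here: 15% is the control rate, the hazard is constant, the test is two-sided at 0.05, allocation is 1:1.

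Hazard λ = −ln(0.85)/3 = 0.0542 per year; 12-month risk = 1 − e^(−0.0542) = 5.27%. D is the sum of expected events in both arms, using λ and HR × λ. Power = Φ(√(D/4) × |ln HR| − 1.96).

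For month 36, four equal waves are taken to have 36, 28, 20 and 12 months of follow-up (spacing assumed).

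| Follow-up | Control events per 1,008 | HR detectable at 80% | Events at HR 0.707 | Power at HR 0.707 |
|---|---|---|---|---|
| 3 years for all | 151 | 0.71 | 261 | 80% |
| Staggered to month 36 | 103 | 0.65 | 177 | 64% |
| 12 months | 53 | 0.54 | 91 | 38% |

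For the 12-month row: √(91/4) × 0.347 − 1.96 = −0.31, and Φ(−0.31) = 0.38. HR 0.707 is the effect implied if the 80% came from 3-year events in independent patients.

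Clustering: 2,016/16 = 126 per team, equal teams assumed, design effect = 1 + 125 × ICC, events divided by it. The documents give no ICC; these values are assumed.

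| ICC | Design effect | Month 36, HR 0.707 | 12 months, HR 0.707 |
|---|---|---|---|
| 0.001 | 1.125 | 58% | 34% |
| 0.005 | 1.625 | 44% | 25% |
| 0.01 | 2.25 | 34% | 20% |

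Teams are unlikely to be equal. An even site split puts 1,008/4 = 252 in each BH team and 1,008/12 = 84 in each VA team, so the size-weighted mean is (4 × 252² + 12 × 84²)/2,016 = 168 and the design effect is 1 + 167 × ICC.

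**The case against.** **The 3-year rate is not a mistake.** It converts directly to an annual hazard of 0.0542, the quantity named for power. This stands: quoting a 3-year incidence is acceptable. What is missing is the follow-up over which that hazard was applied.

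**Clustering and missing data are handled in the analysis.** The plan specifies mixed-effects models, a mixed-effects Cox model and sensitivity analyses for missing data. That is true, and it protects the test. It does not restore the power lost to clustering or attrition, which the sizing does not mention. The 20% and 60% rates concern recruitment, and the 7% in the attrition paragraph is team switching in an earlier study.

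**The power figures rest on assumptions.** They do. A one-sided test would move the detectable hazard ratios to about 0.74, 0.69 and 0.58. If the assumed ICCs refer to 3-year outcomes and are scaled to the lower 12-month risk, 12-month power becomes 37 / 32 / 28% instead of 34 / 25 / 20%. A reader might infer that the trial is underpowered or the 80% false. The documents do not support that: the sponsor's calculation is not shown and may have targeted a larger effect.

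**The counts are approximate and called minimums.** This has some force. A reader might conclude that all the sample figures fail, but 1,008, 2,016 and 2,100 agree exactly. Only 1,100 (hence 2,200) and 265 do not follow.

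**The VA pool may grow.** Eligibility is set by each wave's start date, the registry is updated regularly, and willing decliners may be invited again. A reader might infer that VA recruitment must fail; the documents show a conflict of counts, not a proven shortfall.

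**Conclusion.** The point holds in three parts of unequal strength.

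1. The figures in Number of Subjects are wrong on their own inputs: 1,008 enrolled, not 1,100, and 265 per wave per site matches neither stated total. This needs no assumption.
2. The VA plan conflicts with the stated VA count: 1,600 against 1,100, with about 264 enrolling instead of 504 to 550 if eligible patients divide evenly between arms. This assumes an even control split and a fixed count. The site counts themselves do not sit well with the plan's own percentages and preliminary data.
3. The 80% power is unsupported. At a constant hazard, two-sided and without clustering, the same 1,008 per arm detects anything from HR 0.71 to 0.54 depending on the horizon. If the 80% rests on 3-year events in independent patients, power for that effect falls to about 64% at month 36 or 38% at 12 months, and lower with any positive ICC.

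**What to change.** - **Number of Subjects:** change to about 1,008 per arm (stated as the minimum), 2,016 in total and 252 per wave per site. Reconcile the 250 outreach contacts per site per wave in CHW Intervention with the 2,100 total.
- **Eligible counts:** recheck the BH and VA figures. State whether they are at one date or cumulative over the four waves, and before or after the dual-eligible patients are divided with the other VA study. Then restate the VA targets by arm to fit them.
- **Horizon:** reconcile 12-month follow-up with censoring at end of study and name one horizon for the primary time-to-diabetes analysis. The choice is the sponsor's.
- **Power:** for that horizon, give the expected incidence, the target HR or minimum detectable HR, sidedness, a design effect over a stated ICC range for the unequal teams, an attrition allowance, and the resulting power.

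The cost is protocol wording and a recalculation, with no extra patients. The downside is that the stated power and sample figures will look less favourable.
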